Procedure	Screening a			Inte	rvention	period ((28-day	cycles)				Post-in	tervent	ion follo	ow-up peri	od	Details in CSP section or appendix
	Scr		Cycl	es 1-2			Cycle 3	3	C4-on	wards	ntinued tment)	(# (follow- after las	_	al ftil W)	
Cycle Day	-21 to -1	Day 1	Day 7	Day 8	Day 15	Day 1	Day 7	Day 8	Day 1	Day 8	Study Treatment Discontinued (last dose of study treatment)	30 days	60 days	90 days	180 days (6 months)	Progression/Survival Follow-up (Q8W until 18 months, then Q12W)	
Visit window (± days)	-	-	-	-	± 1	± 3	-	± 1	± 3	± 1	Study Ti	± 3	± 7	± 7	±7	Prog Follo 18 mc	
ECOG performance status ¹	X	X		X		X		X	X		X	X	X	X	X	X	Section 8.2.4
Hepatitis B and C and HIV screening	X																Sections 5.1 and 8.2.5
Safety laboratory assessments (clinical chemistry including TSH, haematology, urinalysis ^{f, k, m})	X	X		X	X	X		X	X	X	X	X	Х	X			Section 8.2.5
Coagulation parameters ⁿ	X									X							Section 8.2.5
Pregnancy test (WOCBP only)°	X	X				X			X			X	X	X			Section 8.2.5
AE	X		+		t every v		nay be	X conducte	d by pho		tied to a vis		\rightarrow				Section 8.3
Concomitant medications	X		+		t every v		nay be	X conducte	d by pho	== ne if not	tied to a vis		\rightarrow				Section 6.5

Procedure	Screening a			Inte	rvention	period ((28-day	cycles)				iod	Details in CSP section or appendix				
	Scr		Cycl	es 1-2			Cycle 3	3	C4-on	wards	ntinued tment)	(#		ty follow-up s after last dose)		al frii W)	
Cycle Day	-21 to -1	Day 1	Day 7	Day 8	Day 15	Day 1	Day 7	Day 8	Day 1	Day 8	Study Treatment Discontinued (last dose of study treatment)	30 days	60 days	90 days	180 days (6 months)	Progression/Survival Follow-up (Q8W until 18 months, then Q12W)	
Visit window (± days)	-	-	-	-	± 1	± 3	-	± 1	± 3	±1	Study T	± 3	±7	± 7	± 7	Proj Folk 18 me	
Tumour imaging (RECIST 1.1; CT/MRI including brain scan at baseline) p, s	Xq					Tumour assessments will be conducted every 8 weeks (±1 week) after start of treatment (C1D1) up to 18 months, then every 12 weeks (±1 week) until objective disease progression per RECIST 1.1. If a patient discontinues without disease progression, RECIST tumour assessments will be performed every 8 weeks for 18 months, then every 12 weeks, thereafter.										Section 8.1.1	
CCI																	

Procedure	Screening a			Inte	rvention	period ((28-day	cycles)				Post-in	tervent	ion follo	w-up peri	od	Details in CSP section or appendix
	Sere		Cycl	es 1-2			Cycle 3		C4-on	wards	ntinued tment)	(# (/ follow- after las		al rtil W)	

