2.3.1.1 Ceralasertib

Data from non-clinical studies and emerging data from the clinical development programme of ceralasertib shows that ceralasertib as monotherapy or in combination with durvalumab has a manageable safety profile in an advanced cancer population. There were no risks identified that would preclude investigation of ceralasertib as monotherapy or in combination with durvalumab in advanced unresectable melanoma.

Identified risks for ceralasertib include anaemia, neutropenia (including febrile neutropenia), thrombocytopenia, nausea, vomiting, diarrhoea, and fatigue/asthenia which have been reported during the clinical use of ceralasertib as monotherapy or in combination with olaparib or durvalumab. Potential risks include myelodysplastic syndrome (MDS)/acute myeloid leukaemia (AML). The emerging safety profile of ceralasertib either as monotherapy or in combination with either olaparib or durvalumab is consistent with preclinical findings and/or the safety profile of the respective combination agent.

Detailed information on the identified and potential risks, including the most commonly observed AEs, for ceralasertib when used alone or in combination are provided in the ceralasertib IB.

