To assess the safety and tolerability of ceralasertib monotherapy and ceralasertib plus durvalumab in patients with unresectable or advanced melanoma and primary or secondary resistance to a PD-(L)1 inhibitor PD-(L)1 inhibitor	Safety and tolerability will be evaluated in terms of adverse events (AEs), vital signs, and clinical laboratory assessments. Assessments related to AEs cover: Occurrence/Frequency Relationship to study treatment as assessed by investigator Common Terminology Criteria for Adverse Events (CTCAE) grade Seriousness Death AEs leading to discontinuation of study treatment AEs leading to dose reduction of ceralasertib AEs leading to dose interruption of durvalumab Vital signs parameters include systolic and diastolic blood pressure, and pulse. Assessments cover: Observed value Absolute change from baseline values over time Vital sign status including change in abnormality (eg, abnormal-clinically significant, abnormal-clinically not significant) from baseline Laboratory parameters include clinical chemistry and haematology parameters as well as urinalysis. Assessments cover: Observed value Absolute and percentage change from baseline values over time Laboratory parameter status including change in abnormality (eg, low, normal, high) from baseline to maximum post-baseline value. Assessments cover: Urinalysis categorisation as collected on the database including change in categorisation from baseline to maximum on-treatment value
Exploratory	

Objectives	Endpoints
· CCI	• CCI
• CCI	· CCI

Objectives	Endpoints
• CCI	
• CCI	• CCI
• CCI	• CCI

The objectives and endpoints for the biopsy sub-study are as follows:

Table 6 Objectives and Endpoints for the Biopsy Sub-Study

Objectives	Endpoints
Primary	
To assess changes in CD8+ T-cell infiltration of tumours induced by ceralasertib monotherapy	 CD8+ T-cells tumour infiltration assessed in baseline, on-treatment and off-treatment tumour biopsies Assessments cover: Observed log₂-transformed value in baseline, on-treatment and off-treatment Absolute change from baseline in log₂- scale
	 in on-treatment and off-treatment samples Fold change from baseline for on-treatment and off-treatment samples
Secondary	
To estimate the effectiveness of ceralasertib plus durvalumab by assessment of ORR, DoR, TTR, change in tumour size, PFS and OS	As described for the main study, using the investigator assessment of tumour response per RECIST 1.1 The analysis will include all dosed patients as dosed,

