4.3.1 Ceralasertib Monotherapy Dose Rationale

The dose of ceralasertib selected for this study (240 mg BD) is primarily based on the clinical results observed in the HUDSON study (D6185C00001), with supportive data on preclinical, translational and clinical pharmacology data/modelling from Study 4 (D5330C00004).

Preliminary PK observations from Study 4 (D5330C00004) showed CCI dose-proportional increase in exposure, where the plasma concentrations following a single dose at 320 mg QD were CCI to that observed at 240 mg QD CCI % overlap in AUC), suggesting the need to change to BD schedules in order to increase ceralasertib exposure beyond the dose of 240 mg QD.

The dose of ceralasertib as monotherapy 240 mg BD for 7 days in 28-day cycles is based on clinical safety and tolerability (mainly bone marrow safety outcomes) and clinical PK/PD data. The dose level of 240 mg BD is predicted to maintain ceralasertib concentrations above the estimated concentration of an inhibitor where ATR catalytic activity is reduced by 90% (IC90) threshold for hours in ceralasertib based on simulations from a preliminary population PK model, and hence, it achieves maximum IC90 daily coverage. In addition, 1-week ceralasertib dosing maximises cytotoxic T-cell (CD8+/Ki67+) proliferative burst (by minimising the time in which proliferative T-cells are depleted) during the three-week off-treatment period, potentially promoting upregulation of PD-(L)1 which can be subsequently blocked with durvalumab to enhance anti-tumour T-cell responses.

Considering emerging PK data from ongoing studies, there is no evidence to indicate any ethnic sensitivity in Asian patients compared to Western patients.

The choice of ceralasertib schedule is supported by preclinical data in syngeneic mouse tumour models in which an intermittent dosing schedule for ceralasertib is most efficacious in terms of balancing the direct anti-tumour effects, the potential for priming an IFN-mediated immune response and dynamic modulation of the tumour immune microenvironment (see ceralasertib IB). An intermittent schedule is also supported by a population PK-PD model describing ceralasertib-induced thrombocytopenia and neutropenia, which showed that at least two-week off-treatment period is needed for platelet/neutrophil recovery. This same model also demonstrated that haematological toxicity is reduced with a 7-day schedule compared to 14-day schedule of ceralasertib.

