9.4.3.2 Other Safety Endpoint(s)

[figure not shown]
Clinical chemistry, haematology, urinalysis, and vital signs will be listed individually by patient and appropriately summarised. For all laboratory variables that are included in the CTCAE (version 5.0), the CTCAE grade will be calculated.

Details of any death will be listed for all patients.

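### The low/normal/high laboratory shift uses the highest post-baseline value, so that one summary is uninformative for the falls in blood counts expected with ceralasertib

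*Protocol*

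**What the plan says.** The safety part of Table 5 (protocol Section 3) sets the scope: "Laboratory parameters include clinical chemistry and haematology parameters as well as urinalysis". Three assessments follow for the laboratory parameters. The first two are the measured result itself and how far it has moved since baseline, in units and in per cent, at successive visits. The third is the shift: "Laboratory parameter status including change in abnormality (eg, low, normal, high) from baseline to maximum post-baseline value".

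Urinalysis then has its own line, also tied to a maximum. Table 6 gives the biopsy sub-study the same safety endpoints as the main study, so the rule carries over.

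Section 2.3.1.1 states the expected toxicity: "Identified risks for ceralasertib include anaemia, neutropenia (including febrile neutropenia), thrombocytopenia, nausea, vomiting, diarrhoea, and fatigue/asthenia". The three risks on that list that are read from a laboratory value are all decreases. On their time course, Section 4.3.1 cites a population model which "showed that at least two-week off-treatment period is needed for platelet/neutrophil recovery".

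Section 9.4.3.2 provides for individual listings and summaries of laboratory data, and adds: "For all laboratory variables that are included in the CTCAE (version 5.0), the CTCAE grade will be calculated". No section names a minimum, or a worst value by direction, for the shift.

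**The concern.** The shift offers three categories, one of which is low, but selects the post-baseline value by a rule that works only for harm in the upward direction. That suits liver enzymes, bilirubin and creatinine. It is the wrong way round for blood counts and albumin, where the maximum is the patient's best value.

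This matters here because the main laboratory risks of ceralasertib are low counts, and dosing is intermittent: seven days on treatment, then 21 days off. Recovery of platelets and neutrophils between courses is part of the dose rationale, and blood is sampled both near dosing and at the next Day 1. The maximum will tend to pick the recovered sample. What is at stake is a per-patient table, normally read as a worst-case classification, that does not classify the worst case for the parameters of most interest.

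**Working it through.** The protocol states no figure that depends on this rule, so there is nothing to reproduce. The check is one of logic, followed by an illustration.

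**Step 1: what the rule does.** Let a patient have *k* post-baseline values of a parameter.

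- The maximum is below the lower limit of normal only if all *k* values are below it.
- The minimum is below the lower limit if any one of the *k* values is.

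The low category therefore means always low under the stated rule and ever low under a minimum rule. This needs no assumption.

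**Step 2: how many values there are.** From the Schedule of Activities (Section 1.3), row "Safety laboratory assessments (clinical chemistry including TSH, haematology, urinalysis", the scheduled visits after first dose in Cycles 1 to 3 are:

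- combination, *k* = 7: C1 D8, D15; C2 D1, D8, D15; C3 D1, D8;
- monotherapy, *k* = 8: C1 D7, D15; C2 D1, D7, D15; C3 D1, D7, D15.

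In each arm, two of these are Day 1 visits, taken after the off-treatment weeks.

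**Step 3: one patient.** The values are assumed: platelets with a reference range of 150 to 400 and a normal baseline, at the eight monotherapy visits: 140, 45, 210, 130, 50, 190, 120, 48. Six of the eight are low. The maximum is 210, so the stated rule tabulates normal to normal. The minimum is 45, which would be tabulated as normal to low.

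**Step 4: illustration across patients.** Suppose each value is low with probability *p*, independently between visits. Both are assumptions; the documents give no such frequency.

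- Share low by the maximum: *p*^*k*.
- Share low by the minimum: 1 − (1 − *p*)^*k*.

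| *p* | Combination, *k* = 7: maximum / minimum | Monotherapy, *k* = 8: maximum / minimum |
|---|---|---|
| 0.1 | 0.0% / 52.2% | 0.0% / 57.0% |
| 0.3 | 0.02% / 91.8% | 0.01% / 94.2% |
| 0.5 | 0.8% / 99.2% | 0.4% / 99.6% |
| 0.7 | 8.2% / 99.98% | 5.8% / 99.99% |
| 0.9 | 47.8% / about 100% | 43.0% / about 100% |

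Independence is a poor description of a regular fall and recovery. A second version fixes every value other than Day 1 as low and lets each of the two Day 1 values be low with chance *r*. The maximum rule then shows *r*² of patients as low: 0% at *r* = 0, 1% at *r* = 0.1 and 9% at *r* = 0.3. The minimum rule shows 100% in each case. This still assumes that the two Day 1 values are independent; positive correlation between them would raise the maximum-rule figure.

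**Step 5: what the recovery statement covers.** Section 4.3.1 speaks of platelets and neutrophils only. It does not say that haemoglobin recovers between cycles. Section 6.6.1 also foresees interruptions of two weeks or more for prolonged anaemia, neutropenia or thrombocytopenia. Patients who stay low throughout are classified as low under either rule.

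**The case against.** The best case on the other side has four parts.

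*The shift is one descriptive output among several.* Observed values and change over time show by visit any fall at Days 7, 8 or 15. Section 9.4.3.2 lists haematology by patient and calculates CTCAE grades. Section 9.4.3.1 summarises adverse events by grade and has a medical expert review laboratory data, with marked haematological abnormalities among the examples. This stands and limits the point. It does not make the shift correct. Summaries over time are not per-patient worst-case classifications, and Section 9.4.3.2 does not specify a grade shift. Section 8.3.5 restricts when a laboratory deterioration is reported as an adverse event, so the adverse event tables are not a complete substitute.

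*No decision rests on it.* Safety is descriptive, the monitoring committee sees all available safety data, and toxicity management works from CTCAE grade. This also stands.

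*The analysis plan may handle direction by parameter.* It may, and the endpoint wording does not forbid a further shift by the minimum. But the protocol is not silent on direction. It names one, and for these parameters it is the wrong one.

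*Maximum might mean worst CTCAE grade.* The wording does not fit that reading: it refers to a value and to low, normal and high categories.

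A reader might infer that cytopenias vanish from the safety evaluation, or that the report would give a false picture of tolerability. The documents do not support this, because the other outputs carry the low counts.

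**Conclusion.** The rule in Table 5 is wrong for every parameter where harm is a decrease, and no other section corrects it. The consequence is limited: the low/normal/high shift summary is uninformative for the main laboratory risks of ceralasertib, while the rest of the safety reporting still shows them.

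The conclusion that low means low at every visit follows from the wording alone. That transient falls would be shown as normal rests on recovery between courses, which the protocol supports for platelets and neutrophils. It would be tempting to say the same of anaemia, but the dose rationale does not mention haemoglobin, and persistently low patients would still appear as low. The percentages depend on assumed probabilities and on independence, and at high assumed values a large minority remains low under the stated rule. They show the mechanism and are not a forecast. Whether the analysis plan repeats the rule cannot be told from the protocol. This is a correction that should be made, of modest weight.

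**What to change.** In the laboratory line of Table 5, replace the reference to the maximum with: *minimum and/or maximum post-baseline value, according to the direction of concern for each parameter*. In practice:

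- minimum for haemoglobin, leukocytes, neutrophils, lymphocytes, platelets and albumin;
- maximum for liver enzymes, bilirubin and creatinine;
- both where either direction matters, for example potassium, sodium, calcium and glucose.

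The list by parameter can sit in the analysis plan; the protocol needs only the general wording. The biopsy sub-study follows through its cross-reference. The cost is one line of text and the matching table shell. No new data are needed, and dosing, visits and patient management are unaffected. If the analysis plan already classifies by the minimum for these parameters, only the protocol wording has to be brought into line.

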4 STUDY DESIGN

4.1 Overall Design

Main study: This is a Phase 2, randomised, open-label, multicentre, international study assessing the efficacy and safety of ceralasertib and ceralasertib plus durvalumab in patients with unresectable or advanced melanoma and primary or secondary resistance to PD-(L)1 inhibition. Patients will be recruited from multiple centres with a global footprint that is expected to include North America, Europe, and Asia.

Approximately 150 patients will be randomised, at a 2:1 randomisation ratio (approximately 100 patients in Arm 1 and approximately 50 patients in Arm 2) to the following intervention groups:

- 1 **Arm 1:** Ceralasertib 240 mg BD Days 1 to 7 plus durvalumab 1500 mg Day 8, Q28D, until progressive disease, unacceptable toxicity, withdrawal of consent, or if a study treatment discontinuation criterion is met.
- 2 **Arm 2:** Ceralasertib 240 mg BD Days 1 to 7, Q28D, until progressive disease, unacceptable toxicity, withdrawal of consent, or if a study treatment discontinuation criterion is met.

Randomisation will be stratified by resistance to prior immune-oncology treatment and baseline LDH expression. At enrolment, investigators will confirm the PD-(L)1 resistance type and whether LDH is normal or above upper limit of normal in order to stratify the patients accordingly. For further details on randomization, refer to Section 6.3.1.

Crossover between treatment arms is not permitted.

Patients must have received at least 1 line of treatment for metastatic disease including an anti-PD1 or anti-PD-(L)1 therapy, or combination of anti-PD1/L1 and anti-CTLA4 and no more than 2 prior regimens in the metastatic setting. All patients must have demonstrated disease progression on anti-PD-(L)1 while on treatment and must have confirmatory scan for progression disease per RECIST 1.1 unless progression is accompanied with clinical deterioration. Patients who progress on adjuvant immunotherapy are also permitted to enrol provided that they progressed on therapy or within 12 weeks after completion of the treatment. Patients with BRAF mutations may have received a BRAF or BRAF plus MEK inhibitor if eligible to do so. All patients must demonstrate disease progression prior to study entry and there must be no intervening therapy eg, investigational agents after completion of prior immunotherapy, except for approved targeted agents for patients with eligible BRAF or c-Kit mutations. For country-specific requirements for France see Appendix K 1.2.

Due to the different schedules of administration of the study treatment options, neither patients nor investigators will be blinded to study treatment assignment. Measures to limit bias are detailed in Section 6.3.

An IDMC comprised of independent experts will be convened to review the unblinded safety and tolerability data and the unblinded efficacy data from the interim analyses and will recommend to the sponsor whether the study should continue unchanged, be stopped, or be modified in any way. Further details on the IDMC are present in Section 9.6.

Number of Patients

Approximately 150 patients are expected to be randomised in total, at a 2:1 randomisation ratio, such that there will be approximately 100 evaluable patients in the ceralasertib and durvalumab combination therapy arm and approximately 50 patients in the ceralasertib monotherapy arm. However, fewer patients may be randomised to any given treatment arm following a recommendation by the IDMC to terminate recruitment to an arm based on safety or lack of efficacy.

Enrolled	Estimated compatients
Randomly assigned	Estimated 150 patients
Evaluable patients	Estimated 150 patients

Biopsy sub-study: An open-label, non-randomised, biopsy sub-study is planned in patients suitable for 3 mandatory biopsies. Patients recruited into the biopsy sub-study will receive 1 cycle of ceralasertib monotherapy (Cycle 0) followed by ceralasertib plus durvalumab from Cycle 1.

The biopsy sub-study is anticipated to recruit patients from pre-defined/selected subset of sites and the estimated number of patients in the biopsy sub-study is as follows:

Enrolled	Estimated patients
Evaluable tumour biopsy patients	Estimated 30 patients

Note: "Enrolled" means a patient's, or their legally acceptable representative's, agreement to participate in a clinical study following completion of the informed consent process. Potential patients who are screened for the purpose of determining eligibility for the study, but are not randomised/assigned in the study, are considered "screen failures", unless otherwise specified by the protocol. For country-specific requirements for Germany see Appendix K 1.3.

Serial tumour biopsies are mandated in the patients recruited into the biopsy sub-study and will be taken at baseline during the screening period, during treatment with ceralasertib monotherapy and during the off-treatment period of ceralasertib monotherapy.

During the Cycle 0 treatment period, patients will be treated with ceralasertib 240 mg BD Days 1 to 7, followed by an off-treatment period between Days 8 to 28. From Cycle 1 onwards, patients will be treated with the combination of ceralasertib 240 mg BD Days 1 to 7 plus durvalumab 1500 mg Day 8, Q28D, until progressive disease, unacceptable toxicity, withdrawal of consent, or if a study treatment discontinuation criterion is met.

For dose modification recommendation, stopping rules and discontinuation for ceralasertib monotherapy or in combination with durvalumab, please refer guidance for the main study (Section 6.6).

4.1.1 Study Conduct Mitigation During Study Disruptions Due to Cases of Civil Crisis, Natural Disaster, or Public Health Crisis

The guidance given below supersedes instructions provided elsewhere in this CSP and should be implemented only during cases of civil crisis, natural disaster or public health crisis (eg, during quarantines and resulting site closures, regional travel restrictions and considerations if site personnel or study patients become infected with severe acute respiratory syndrome coronavirus 2 [SARS-CoV-2] or similar pandemic infection), which would prevent the conduct of study-related activities at study sites, thereby compromising the study site staff's ability to conduct the study or the patient's ability to participate in the study. The investigator or designee should contact the study sponsor to discuss whether the mitigation plans below should be implemented.

To ensure continuity of the clinical study during a civil crisis, natural disaster, or public health crisis, changes may be implemented to ensure the safety of study patients, maintain compliance with GCP, and minimise risks to study integrity.

Where allowable by local health authorities, ethics committees, health care provider guidelines (eg, hospital policies) or local government, these changes may include the following options:

- Obtaining consent for the mitigation procedures (note, in the case of verbal consent, the ICF should be signed at the patient's next contact with the study site).
- Rescreening: Additional rescreening for screen failures and to confirm eligibility to participate in the clinical study can be performed in previously screened patients. The investigator should confirm this with the designated AstraZeneca clinical lead.
- Home or Remote visit: Performed by a site-qualified HCP or HCP provided by a TPV.
- Telemedicine visit: Remote contact with the patients using telecommunications technology including phone calls, virtual or video visits, and mobile health devices.

If a site visit is not possible, at home delivery and administration of study treatment may be performed.

For further details on study conduct during civil crisis, natural disaster, or public health crisis, refer to Appendix H.

